5. GENERAL METHODOLOGY AND CONVENTIONS

5.1. Hypotheses and Decision Rules

There is no statistical hypothesis testing in the OLE period for this study.

5.2. General Methods

5.2.1. Analyses for Continuous Endpoints

Descriptive statistics will be provided for continuous variables using number of subjects (N), mean, standard deviation (SD), median, and range.

5.2.2. Analyses for Categorical Endpoints

Frequency and percentage for each category of the variable will be provided as a descriptive summary for each visit.

5.2.3. Analyses for Time-to-Event Endpoints

Not applicable.

5.3. Methods to Manage Missing Data

Missing reference value in calculating primary endpoint of AHV is specified in Section 3.1. The missing data for the post-baseline data of the primary endpoint and all secondary efficacy endpoints will not be imputed and be summarized as observed data.

Missing safety data will be handled according to the Pfizer Clinical Data Interchange Standards Consortium (CDISC) safety rulebook and data standard rules for imputation, including missing dates (when the date is required for a calculation) and missing severity of adverse events.

6. ANALYSES AND SUMMARIES

There are two treatment groups in the OLE, defined as originally randomized to somatropin and originally randomized to Genotropin® in the main study.

6.1. Efficacy Endpoint

6.1.1. Main Analysis

- Estimand strategy: Treatment policy strategy for AHV every 12 months, as well as for absolute value and change from baseline for each of the efficacy endpoints, including height SDS, IGF-1 and IGF-1 SDS, IGFBP-3 and IGFBP-3 SDS, BM, LH, FSH and testosterone or estradiol.
- Analysis set: FAS (defined in [Section 4](#)).
- Analysis methodology: change from baseline to OLE Year 1, Year 2, Year 3, etc., will be descriptively and graphically summarized.
- Intercurrent events: Data after study drug discontinuation will be included.
- Descriptive summary includes N, mean, SD, median, minimum, and maximum for absolute value. It can be presented by treatment group (originally randomized to somatropin, originally randomized to Genotropin®, and total), by ADA sub-groups including ADA status (positive or negative), ADA titers, and by visit.

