### 4.1 INCLUSION CRITERIA

Patients must meet all inclusion criteria to be eligible for the main study:

1. Pre-pubertal children aged  $\geq 3$  yrs old and not yet 11 years for girls (10 years and 364 days) or not yet 12 years (11 years and 364 days) for boys (on the date of ICF signature) with either isolated GHD, or GH insufficiency as part of multiple pituitary hormone deficiencies.
2. Confirmed diagnosis of GHD by 2 different GH provocation tests defined as a peak plasma GH level of  $\leq 10$  ng/ml, determined by local (if done prior to signing the ICF) or central laboratory using a validated assaya. Prior local laboratory results will be accepted subject to pre-approval by global study MM and if the tests were conducted according to one of the protocols in [Appendix Bb](#).
3. BA is not older than CA and should be  $< 10$  for females and  $< 11$  for males.
4. No prior exposure to any r-hGH therapy.
5. Impaired Ht and HV defined as:
  - Annualized HV below the 25th percentile for CA (HV  $< -0.7$  SDS) and gender according to the OPKO HV (Tanner, Prader and Hermanussen) calculator, provided.
  - The interval between 2 Ht measurements should be at least 6 months, but should not exceed 18 months prior to inclusion.
6. Baseline IGF-1 level of at least 1 SD below the mean IGF-1 level standardized for age and sex (IGF-1 SDS  $\leq -1$ )c according to the central laboratory reference values. A single re-test will be allowed (subject to discussion with MM) if all other criteria are met.
7. Normal calculated GFR based on updated “bedside” Schwartz formula for pediatric patients (recommended calculation is provided below):
 
$$\text{CrCL (mL/min/1.73 m}^2\text{)} = 0.413 * \text{Ht} / \text{Scr};$$

Ht: in cm;  
Scr: mg/dL;

a ITT, with serum cortisol response to hypoglycemia if insulin stimulation test is chosen / Arginine test / Clonidine test / Glucagon test / L-dopa test.

b Prior spontaneous nocturnal GH secretion should be  $\leq 10$  ng/mL.

c According to rounding policy IGF-1 results  $\leq -0.95$  **might** be acceptable as well.

Effective Date: Date of final electronic approval

8. Children with multiple hormonal deficiencies must be on stable replacement therapies (no change in dose) for other hypothalamo-pituitary-organ axes for at least 3 months prior ICF signing.
9. Normal 46XX karyotype for girls.

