#### 5.1 VISIT 1 - SCREENING PERIOD (DAY – 56 TO DAY -1)

The screening period will last up to 8 wksb and can be conducted over several visits prior to randomization, to minimize blood volume withdrawals per visit. Screening visits are intended to collect current clinical data and to perform all required investigations needed to establish a patient's eligibility for the study. Prior to any study specific assessments, written assent from pediatric patients (where applicable based on age and country) and consent from the parent(s) or legal guardian(s) will be obtained. Upon completion of the Informed Consent process and obtaining written consent from the parent(s) or legal guardians(s) a patient is deemed to be 'enrolled into the study'.

The following assessments will be conducted at these screening visits:

- Inclusion/exclusion verification.
- Parental Htc, and patients' Ht, Ht SDS, HV and HV SDS.
- Body weight and BMI SDS.
- Medical history, including a description of pituitary deficiencies, concomitant and previous medications.
- Overall health status assessment, including complete physical examination and vital signs.
- Pubertal status (according to Tanner stages).

a Illiterate patients should provide their consent in a method that is accepted according to local regulations.

b If the patient's screening process is delayed because of a benign illness or unforeseen benign condition (i.e. pharyngitis, viral GI problems, minor accident or trauma, etc.) or other technical issue that is related screening procedures (for example, delays with laboratory results) extra time will be added to the duration of the screening period, but not in excess of an additional four wks (total of 12 wks screening period).

c It's recommended that parents will be measured at the site. If measured parental Ht is not available an estimate should be provided by the parent. It should also be noted that the patient's birth date is required for accurately reporting of Ht SDS.

Effective Date: Date of final electronic approval

- BAa determination with the method of Greulich-Pyle using a central BA reader.
- Assessment of biochemical markers and stimulation tests:

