### 5.2.1 Visit 2 (Day 1/Baseline) – recommended injection days as indicated in [Appendix E](#)

Visit 2 must be conducted within 2 wks of randomization.

The following assessments will be conducted on Day 1/Baseline:

a 1. Western Europe, Israel, Australia, New Zealand, Canada and USA; 2. Central and Eastern Europe, Greece, Turkey, Latin America and Asia except for India and Vietnam 3. India and Vietnam.

b All visits, except Visit 3, can be conducted within the specified window to accommodate patient availability, but must be conducted on day 4 (-1) post dose.

c Applicable only for MOD-4023, Visit 3 assessments, if conducted on Day 14 (dosing day), should be done prior to dosing.

Effective Date: Date of final electronic approval

- Auxology measurements: Actual Ht (mean of three consecutive measurements) measured on a calibrated wall mounted stadiometer.
- AEs, local tolerability (aligned with Appendix H), and concomitant medications.
- Overall health status assessment, including complete physical examination and vital signs.
- Safety laboratory tests: chemistry, hematology and urinalysis.
- Pubertal status (according to Tanner stages).
- Assessment of thyroid function and biochemical markers: TSH, FT4, IGF-1, IGF-1 SDS, IGFBP-3 and IGFBP-3 SDS serum levels.
- Assessment of MOD-4023 serum levels (applicable for MOD-4023 arm only).
- Parameters of glucose metabolism: overnight fasting glucose, overnight fasting insulin, HbA1c.
- Parameters of lipid metabolism: overnight fasting cholesterol, triglycerides, HDL, LDL, Lp(a), FFA.
- Assessment of anti-MOD 4023 and anti-hGH Ab (depending on arm of study).
- BAa.
- ECG pre-dosing.
- Training for patients, parents or legal guardians on drug administration.
- Fundoscopy (if there are signs or symptoms indicative of benign intracranial hypertension).
- Training for patients, parents or caregiver for completing the PAT assessment.
- Administration of study drug at the study site by patient or parent/caregiver.
- MOD-4023 on-site OAT assessment (USA only).
- MOD-4023 on-site PAT assessment (USA only).
- QoL Questionnaire completion (in specific countries as indicated in [Appendix L](#)).
- Drug dispensing and accountability.

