### 5.2.5 Visit 5 (Month 3/Wk 13 [ $\pm 1$ wk]), Visit 6 (Month 6/Wk 26 [ $\pm 1$ wk]), Visit 7 (Month 9/Wk 39 [ $\pm 1$ wk]), Visit 8 (Month 12/Wk 52 [ $\pm 1$ wk])

The following assessments will be conducted at Visits 5, 6, 7 and 8 on Day 4 (-1) post dose:

- Auxology measurements: Actual Ht (mean of three consecutive measurements) measured on a calibrated wall mounted stadiometer.
- AEs, local tolerability, and concomitant medications.
- Overall health status assessment, including complete physical examination and vital signs.
- Safety laboratory tests: chemistry, hematology and urinalysis.
- Pubertal status (according to Tanner stages);
- Urine pregnancy test at every visit once a female patient reports first menstrual cycle (menarche).
- Assessment of thyroid function and biochemical markers: TSH, FT4, IGF-1, IGF-1 SDS, IGFBP-3 and IGFBP-3 SDS serum levels.
- Parameters of glucose metabolism: overnight fasting glucose, overnight fasting insulin, HbA1c.
- Parameters of lipid metabolism: overnight fasting cholesterol, triglycerides, HDL, LDL, Lp(a), FFA.

a For the Genotropin® arm a visit by phone interview will be conducted as described in [Appendix I](#).

- Fundoscopy (ONLY if there are signs or symptoms indicative of increased intracranial hypertension).
- BA at Visit 8 only.
- Individual dose adjustment every three months.
- Drug dispensing and accountability.
- MOD-4023 serum levels (MOD 4023 patients only).
- Anti-hGH Ab (Genotropin® patients only).
- ECG (Visit 6 only for Genotropin® patients). Patients in the Genotropin® arm will be requested to inject the study drug preferably at night and come to the clinic the following day for ECG assessment.
- Return of used and unused injection devices and diary cards.
- Return of completed PAT forms (USA only) (Visit 5 only) (applicable for MOD-4023 arm only).
- Anti-MOD-4023 Ab (Visits 5 and 7, MOD-4023 arm only, Visit 8 both arms).
- Informed consent for the LT-OLE (Visit 7 (preferred) or 8).
- QoL questionnaire (QoLISSY) at Visit 8 only.
- For males that are 13 years and older: LH, FSH and testosterone. For females that are 12 years and older: LH, FSH and estradiol (Visit 8 only).

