### 5.10 PUBERTAL ASSESSMENT

Patients may enter puberty during the course of the study and contraception might become relevant. The puberty state is evaluated on routine basis as described above. Once a female patient reports first menstrual cycle (menarche) study sites should perform urine pregnancy test at every visit.

For a female child, even though she is pre-pubertal at enrollment, it is possible that she may enter puberty during the course of the study and could theoretically become pregnant. As she cannot continue in the study if she were to become pregnant, the investigator or delegated study staff is obligated to discuss this issue ahead of time with the patient and her parents/legal guardian. Patients must refrain from sexual activity during the study i.e. observe complete sexual abstinence as the only acceptable contraceptive measure in this study.

If a patient were to become pregnant or thinks she may have become pregnant during the study, the Investigator should be informed immediately, such information will be recorded in study documentation and the patient will be asked to stop taking the study medication as it may cause unforeseen risks to the unborn baby. Serum pregnancy test will be scheduled immediately in such

cases, and in the case of the negative result the test should be repeated in two wks to confirm or exclude the pregnancy.

In case of negative test results confirmed by the second negative test result, based on the Investigator's recommendation, the Sponsor may allow the patient to return to the full study schedule with guidance from Sponsor, if applicable. or the patient will be offered to remain in the study without study medication, but to complete the remaining study procedures as scheduled (missed visits are recommended to be realized).

All pregnancy tests used in this study, either urine or serum, must have a sensitivity of at least 25 mIU/mL and must be performed by a certified laboratory. Pregnancy tests will also be done whenever one menstrual cycle is missed during treatment (main study and LT-OLE) and when potential pregnancy is otherwise suspected and may be repeated if requested by institutional review boards (IRBs)/ethics committees (ECs) or if required by local regulations. In the case of a positive confirmed pregnancy, the patient will be withdrawn from administration of investigational product but may remain in the study for follow up.

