3.4. Baseline Variables

Baseline is defined as the main period baseline for efficacy and biomarker assessment. Except the reference visit for AHV, is defined in Section 3.1 as the values at the previous 12 month in the OLE period.

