6.3. Subset Analyses

There is no planned subset analysis for this study.

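### Extension SAP: change in LH, FSH and sex steroids is taken from a baseline at which no child has a value; separately, yearly mean height velocity pools prepubertal and pubertal children

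*SAP*

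**What the plan says.** **Hormones.** SAP 6.1.1 applies the treatment-policy strategy to AHV every 12 months, "as well as for absolute value and change from baseline for each of the efficacy endpoints, including height SDS". The same list continues through IGF-1, IGFBP-3 and bone maturation to LH, FSH and testosterone or estradiol. SAP 3.4 fixes the reference point: "Baseline is defined as the main period baseline for efficacy and biomarker assessment", with an exception only for the AHV reference visit. SAP 2.1.1 says something different for the same variables: absolute values at each visit and/or change from the previous interval.

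In the main study the protocol (5.2.5) restricts the draw by age and visit: "For females that are 12 years and older: LH, FSH and estradiol (Visit 8 only"; the same bullet sets 13 years for boys. The Appendix A flow chart agrees, with one mark at Visit 8/10 and none at screening or Visit 2. In the extension the tests are annual with the same age limits (SAP 3.3.1).

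**Growth.** Children are prepubertal at consent, "not yet 11 years for girls (10 years and 364 days) or not yet 12 years (11 years and 364 days) for boys" (Protocol 4.1). Protocol 5.10 expects that to change: "Patients may enter puberty during the course of the study". The extension is open-ended, and the SAP windows in Appendix 2.1 run to OLE Year 4. Tanner stage is recorded at Visit 8/10 and then every 12 months. SAP 6.1.1 offers breakdowns by original arm, ADA status, ADA titer and visit. SAP 6.1.2 has no supplementary analysis, and SAP 6.3 states: "There is no planned subset analysis for this study".

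**The concern.** The hormone change is an output that cannot exist if its baseline was never measured. A programmer following 6.1.1 and 3.4 would produce an empty table, or would have to choose another baseline after the data are in.

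The growth point is separate. AHV is in cm/year, with no correction for age, sex or maturity. If pubertal children grow at a different rate from prepubertal ones, the yearly mean moves as the mix moves, even when the response within each group is constant. A waning response could be masked, or a rise credited to long-term treatment. Long-term efficacy is an objective of the extension, and the yearly AHV means are what a reader will use to judge it.

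**Working it through.** The extension has no hypothesis test and no sample size (SAP 5.1), so there is no plan figure to reproduce. The checks are age arithmetic and a simple mixture calculation.

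**1. Can any child have a main-baseline hormone value?**

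Inputs:
- Consent age: girls under 11, boys under 12 (Protocol 4.1).
- Longest screening: "but not in excess of an additional four wks (total of 12 wks screening period" (Protocol 5.1).
- Eligibility to randomization: 7 days, a recommendation only (Protocol 5.1).
- Randomization to baseline: "Visit 2 must be conducted within 2 wks of randomization" (Protocol 5.2.1).
- Flow chart alternative: baseline up to 4 weeks from eligibility (Appendix A).

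Formula: oldest age at Visit 2 = consent limit + weeks/52.18.

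| Path to Visit 2 | Weeks | Girls | Boys |
|---|---|---|---|
| 12 + 1 + 2 | 15 | 11.29 | 12.29 |
| 12 + 4 (flow chart) | 16 | 11.31 | 12.31 |
| Needed for the test | | 12 | 13 |

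A child would need about a year between consent and baseline to qualify; the protocol allows about 16 weeks. No draw is scheduled at Visit 2 in any case. Children with a main-baseline value: **0**.

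At Visit 8 (week 53 at the latest) the limits are 11.31 + 53/52.18 = 12.32 for girls and 13.32 for boys, so only the oldest entrants have a value even there. Assuming ages uniform over the entry range, that is 0–4%. A boy would need to be about 11.7–11.8 years at consent (13 − 68/52.18 = 11.70; 13 − 63/52.18 = 11.79).

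**2. How fast does the mix shift?**

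(a) Using only the protocol's ages, with the hormone-test age as a proxy for puberty. Assumptions: consent age uniform (girls 3–11, boys 3–12), no withdrawals, 0–16 weeks from consent to baseline. At the end of OLE Year k, share = (k + weeks/52.18)/8 for girls and the same over 9 for boys.

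(b) Using assumed puberty onset: SD 1 year; mean 10.5 (girls) and 11.5 (boys), or 12 and 13 if delayed; 30% girls; uniform entry age; prepubertal at entry; no withdrawals. Simulated with 400,000 children.

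| Time | (a) Girls 12+ | (a) Boys 13+ | (b) Pubertal, both sexes |
|---|---|---|---|
| Month 12 | 0–4% | 0–3% | 4–10% |
| OLE Year 1 | 13–16% | 11–15% | 12–23% |
| OLE Year 2 | 25–29% | 22–26% | 22–35% |
| OLE Year 3 | 38–41% | 33–37% | 34–48% |
| OLE Year 4 | 50–54% | 44–48% | 46–60% |

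**3. What could that do to mean AHV?** Shift = share × (pubertal minus prepubertal velocity). The documents do not give that difference; take 1–4 cm/year as an assumed range. Under (a) the share grows between Year 1 and Year 4 by 3/8 = 37.5 points in girls and 3/9 = 33.3 points in boys. The pooled mean would then drift by 0.38–1.5 cm/year (girls) or 0.33–1.33 cm/year (boys) with no change in response. This shows the mechanism; it does not estimate bias.

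**4. Why use Tanner stage at both ends of the interval?** Under (b), the fraction of children at Tanner II–V at the end of OLE Year 1 who entered puberty during that year is (22.7 − 10.4)/22.7 = 54% with earlier onset and (11.7 − 3.7)/11.7 = 68% with later onset. A split on end-of-interval stage alone would label much prepubertal growth as pubertal.

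**The case against.** **On hormones.** Absolute values are still planned, and change from the previous interval (SAP 2.1.1) becomes computable once a child has two annual tests. SAP 3.3.1 also files these hormones under other endpoints, whereas the 3.4 baseline is for efficacy and biomarkers. This stands as a limit: a reader might infer that the hormone analysis returns nothing at all, and that is not so. It does not rescue the planned change. Section 6.1.1 calls the hormones efficacy endpoints and names change from baseline. If 3.4 applies, the result is empty; if it does not, no baseline is defined. Section 2.1.1 conflicts with this and does not cure it.

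**On growth.** Five arguments have weight.
- Tanner stage and bone age are collected yearly, and pubertal status is itself a listed variable in SAP 2.1.1, so its distribution may appear beside AHV.
- Height SDS is standardised for age and sex (SAP 3.1.2), and so is IGF-1 SDS. That removes the average age-related spurt and leaves mainly differences in pubertal timing.
- The extension is single-arm and descriptive. Its two groups come from randomization, so their pubertal mix should be similar. Without a control, a Tanner table cannot attribute growth to the drug.
- Withdrawal at the bone-age limits or for slow growth (Protocol 4.4) removes some of the most mature children, so the no-withdrawal shares may be too high. Year 4 is a programming window, not a promised duration.
- The table list in SAP Appendix 6 is redacted and the 6.1.1 wording on breakdowns is permissive, so a Tanner table cannot be excluded.

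These points limit the growth concern to AHV and to a recommendation. They do not remove it: the readable text of 6.1.1, 6.1.2 and 6.3 specifies no growth summary by pubertal stage.

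**Conclusion.** Two separate conclusions.

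1. **Hormone change from main baseline is wrong as written.** It has N = 0 by schedule and by age, whatever the accrual or dropout, and it conflicts with SAP 2.1.1. No outside assumption is needed. The harm is modest because absolute values remain.

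2. **Splitting AHV by pubertal status is a worthwhile, low-cost addition.** As planned, year-to-year change in mean AHV mixes treatment response with a changing pubertal mix. The problem is small in OLE Year 1 and grows later. Height SDS and IGF-1 SDS are less affected. The shares rest on uniform entry ages, assumed onset ages and no withdrawals.

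A reader might infer that long-term growth on somatrogon cannot be told from the pubertal spurt. The documents do not support that: the limit is in the planned summaries, not in the data. Nor does the missing hormone baseline cause the mixing in AHV; the two defects are independent. The illustrative drift should not be set against the 1.8 cm/year margin either, since that margin governs a between-arm comparison in the main study.

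**What to change.** **SAP 6.1.1, with 2.1.1 and 3.4.** Remove change from main-period baseline for LH, FSH, testosterone and estradiol. Report absolute values by sex and Tanner stage, and change from each child's first measured value or from the previous annual value, the latter matching 2.1.1. State which one, and make the three sections agree.

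**SAP 6.1.1 and 6.3.** For each OLE year add a descriptive summary of AHV and height SDS in three groups: Tanner I at both start and end of the interval; entered puberty during the interval; Tanner II–V at the start. Split by sex where numbers allow. Say how a child is classed when the AHV reference is an anchor visit (SAP 3.1.1), since extension Tanner staging is annual only.

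**Cost.** SAP wording and a few descriptive tables from data already scheduled; no visits, tests or sample size change. The downside is small cells early on. With all 220 children continuing and 30% girls (66), assumption (b) gives only about 8–16 pubertal girls at OLE Year 1 (66 × 12.5% = 8.3; 66 × 24.8% = 16.4), so pooling the sexes may be needed in that year.

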6.1.2. Sensitivity/Supplementary Analyses

Not applicable.

6.2. Other Endpoint(s)

6.2.1. Immunogenicity (Antibodies)

Frequency and percentage of anti-somatogon antibodies in FAS will be reported by year and visit, if adequate data are collected.

6.3. Subset Analyses

There is no planned subset analysis for this study.

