**4.4 REMOVAL, REPLACEMENT, OR EARLY WITHDRAWAL OF PATIENTS FROM THERAPY OR ASSESSMENT**

Patients are free to discontinue their participation in the study at any time and without prejudice to further treatment. The investigator must withdraw any patient from the study if that patient or parent/legal guardian requests to be withdrawn. Patients withdrawn from the study during the 12 months of treatment post first dose will not be replaced. Those patients withdrawn who have successfully completed screening, but prior to first dose, will be replaced.

The patient's participation in this study may be discontinued due to the following reasons:

- Request from regulatory agency, sponsor, primary care physician, or Investigator.
- Withdrawal of the patient's/parent's/legal guardian's consent for any additional study participation or procedure, including lost to follow up (with specific withdrawal reason collected, as possible).
- AE:
  - Occurrence of a malignancy during the course of the study.
  - Development of serious intercurrent critical illness.
  - Development of benign intracranial hypertension, if the symptoms return following resumption of drug (after a temporary stop).
  - Occurrence of AEs following which the Investigator, or the patient wishes to discontinue treatment (such as, but not limited to, slipped capital femoral epiphysis, scoliosis, avascular necrosis and development of lipoatrophy, etc.).
- Intake of prohibited concomitant medication (in consultation with the MM).
- Investigator decides that withdrawal from the study is in the best interest of the patient e.g. patient non-compliance, occurrence of neutralizing Ab, protocol deviation(s) (including protocol deviation(s) that affect patient safety and accuracy, and/or validity of data) etc.
- Any clinically significant change in the patient's medical condition.

During the LT-OLE:

- Girls with a BA of  $\geq 13.5$  years and boys with a BA of  $\geq 16$  years.

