- Positive urine pregnancy test or confirmed pregnancy. In case of pregnancy, the study drug should be discontinued, and the Global Study MM be alerted immediately. All pregnancy tests used in this study, either urine or serum, must have a sensitivity of at least 25 mIU/mL and must be performed by a certified laboratory. Pregnancy tests will also be done whenever one menstrual cycle is missed during treatment (main study and LT-OLE) and when potential pregnancy is otherwise suspected and may be repeated if requested by institutional review boards (IRBs)/ethics committees (ECs) or if required by local regulations. In the case of a positive confirmed pregnancy, the patient will be withdrawn from administration of investigational product but may remain in the study for follow up.
- When the patient's annualized growth rate is  $\leq 2$  cm/12 months (the interval between two height measurements should be at least six months).

Patients can be re-screened for inclusion in the main study **one** time. Any data collected during the original screening period will be acceptable as historical data, EXCEPT safety laboratory data and IGF-1 and IGFBP-3 levels, which must be repeated and evaluated for eligibility. In this case, the patient will be assigned a new screening number.

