### 5.5 EARLY DISCONTINUATION STUDY VISIT

If, during the main study, a patient discontinues prematurely from the study for the reasons specified in Section 4.4, the same procedures planned for Visit 8 (12 months/Wk 52 [ $\pm$ 1 wk]) will be conducted. Other procedures and evaluations will be completed as deemed necessary by the Investigator.

If, during the LT-OLE, a patient discontinues prematurely from the study for the reasons specified in Section 4.4, the same procedures for LT-OLE EOS/ET will be conducted.

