2.1.1. Estimand(s)

The estimand of this study uses the treatment policy strategy and estimates the effect for all participants treated regardless of whether an intercurrent event occurs. Each of them includes the following four attributes:

- Population: All patients who entered OLE period and had at least one dose of somatropin;
- Variable:
 - Annualized height velocity (AHV) at each 12-month interval (cm/year)
 - Height standard deviation score (SDS) and change in height SDS;
 - Change in bone maturation (BM);
 - IGF-1 and IGF-1 SDS levels on day 4 (-1) after somatropin dosing across study visits;
 - IGFBP-3 levels and IGFBP-3 SDS on day 4 (-1) after somatropin dosing across study visits;
 - Pubertal status (according to Tanner stages);
 - For males that are 13 years and older: luteinizing hormone (LH), follicle-stimulating hormone (FSH) and testosterone;

- For females that are 12 years and older: LH, FSH and estradiol
- Intercurrent event: All data after an intercurrent event (discontinuation of treatment, discontinuation of study, etc.), if collected, will be included;
- Population-level summary: descriptive summary for absolute values at each visit and/or change from previous interval.

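### The yearly AHV means in the LT-OLE describe children still in the study, although SAP 2.1.1 claims an effect for every treated participant

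*SAP*

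**What the plan says.** **Leaving the LT-OLE.** Protocol 4.4 opens its list with "participation in this study may be discontinued due to the following reasons". For the extension it adds a bone age of at least 13.5 years (girls) or 16 years (boys). It also adds a growth rule that begins "When the patient's annualized growth rate is", sets the limit at 2 cm per 12 months or less, and requires that "the interval between two height measurements should be at least six months". For an LT-OLE leaver, Protocol 5.5 says "the same procedures for LT-OLE EOS/ET will be conducted". Protocol 5.4 lists a height among those procedures, followed by a safety phone call at 30 days. No later height is scheduled.

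**Estimand.** SAP 2.1.1 takes as its population everyone who entered the extension and had at least one dose. It says its treatment-policy strategy "estimates the effect for all participants treated regardless of whether an intercurrent event occurs". It names leaving the study as an intercurrent event and uses later data only where they were collected.

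**Analysis.** SAP 3.1.1 computes AHV from the Month 12 visits of the current and the prior year. SAP 5.3 says missing post-baseline values "will not be imputed and be summarized as observed data". SAP 6.1.1 summarises by OLE year, with splits by original treatment, antibody status and titer, and visit. SAP 6.1.2 marks sensitivity analysis as not applicable, and SAP 6.3 says "There is no planned subset analysis for this study".

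**Protocol rule for leavers.** Protocol 8.3 and 8.6.5 summarise the last available data of children who leave the extension early and compute their height velocity from it. The SAP has no such rule.

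**The concern.** One exit rule is the endpoint itself, and the other follows skeletal maturity, which is closely tied to growth. The outcome therefore helps decide who contributes to the next yearly mean, and the children lost tend to be the slower growers. A mean over those left is not the treatment-policy quantity named in SAP 2.1.1.

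The LT-OLE exists to show long-term efficacy and safety, and Protocol 8.6.5 puts the effect of long-term treatment on annual height velocity in its primary goal. The results are to be tabulated and plotted by year. A reader who trusts the estimand label will take each point as the growth of all treated children. Part of any flattening in the expected decline could then be read as durability when it reflects who stayed.

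**Working it through.** **1. The plan's own figures.** The documents give no mean, exit rate or computed figure for the extension. The one number borrowed here is the SD of 2.5 cm/year from the main-study sample size (Protocol 8.1). That calculation reproduces: 2 × 2.5² × (1.960 + 0.842)² / (1.8 − 0.8)² = 98.1, so 99 per group against the stated 100. Power at 100 per group is 80.7%, and 99/0.9 = 110 randomised per group. None of this is in dispute.

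**2. One child followed through both documents.** Suppose a child leaves at Visit 14 (Month 18) because growth from Month 12 to Month 18 was slow.
- Protocol 5.4 and 8.6.5: the exit visit gives a height, and the height velocity is (Ht at Month 18 − Ht at Month 12)/0.5 year. The low value counts in that year.
- SAP 3.1.1 and 5.3: AHV for OLE Year 1 needs Visit 16, which does not take place. The anchor logic replaces only a missing reference (prior-year) visit, not a missing current-year visit, and nothing is imputed. The child has no AHV for that year or any later one.
- A child who leaves at Visit 16 itself has a Year 1 AHV and is absent from Year 2 on, under either document.

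**3. Slow growers leave before the yearly visit.** Assume AHV is normal and every child at or below 2 cm/year leaves. The upward shift in the mean of those left is SD × φ(a)/(1 − Φ(a)), with a = (2 − mean)/SD. For mean 4 and SD 2.5, a = −0.8, and 2.5 × 0.290/0.788 = 0.92.

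| True mean (cm/year) | SD 2.5: leave | SD 2.5: shift | SD 1.5: shift |
|---|---|---|---|
| 7 | 2.3% | +0.14 | +0.00 |
| 6 | 5.5% | +0.29 | +0.02 |
| 5 | 11.5% | +0.55 | +0.08 |
| 4 | 21.2% | +0.92 | +0.27 |

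**4. Leavers count in their exit year and are absent afterwards.** This was simulated over four yearly means. The assumptions were true means of 8, 7, 6, 5 or 8, 6.5, 5, 4 cm/year; within-child correlation 0.3 or 0.6; and bone-age exit of about 0 to 10% per year from year 2, more likely in slower growers.
- Second yearly mean: at most about 0.04 cm/year too high.
- Fourth yearly mean, SD 1.5: 0.01 to 0.15 too high.
- Fourth yearly mean, SD 2.5: 0.14 to 0.50 too high. At the top of this range a true decline of 4.0 appears as 3.5, with 71% still in the study.

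**5. When bone age can matter.** Entry bone age is below 10 (girls) and 11 (boys) under Protocol 4.1, so the exit values are more than 3.5 and 5.0 bone-age years away. OLE Year 4 starts four years after baseline. By then, under an assumed rate of bone-age advance:
- 1.0 per year (gain 4.0): no boy has reached 16, and only girls entering at 9.5 or more have reached 13.5.
- 1.25 per year (gain 5.0): still no boy, and girls entering at 8.5 or more.
- 1.5 per year (gain 6.0): boys entering at 10.0 or more, and girls at 7.5 or more.

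**The case against.** The case for leaving the plan alone has several sound parts. Exit is permissive. SAP 2.1.1 limits post-exit data to what was collected, and Protocol 4.5 encourages continued follow-up visits, so later heights are not ruled out. Bone age is read yearly, normally at the visit that also records height, so most bone-age leavers would have that year's AHV. N accompanies every summary, and SAP 6.4.2 reports reasons for leaving, completion of each OLE year and numbers reaching final height. Change in height SDS, standardised for age and sex, is reported beside AHV. SAP 5.1 rules out hypothesis tests.

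These points limit the size and the consequence, but they do not make the label right. Counts show how many left, not how they were growing. Protocol 4.5 sets only a minimum of one height at 12 months of the initial treatment period, and nothing schedules heights after an LT-OLE exit. The strongest counterpoint, the protocol's last-measure rule, is absent from the SAP and would cover only the exit year.

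A reader might go further and infer that the Year 3 or Year 4 mean describes younger, still-growing survivors. For example, take two equal age groups growing at a constant 7.0 and 5.0 cm/year. Keeping 90% of the younger and 70%, 50% or 30% of the older raises the mean from 6.0 by about 0.1 to 0.5. The arithmetic is right, but the documents give no such retention, and step 5 suggests few bone-age exits before OLE Year 4 unless bone age advances quickly.

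A reader might also blame the absence of subset analysis. That is not the cause: tables by entry age would show a shift in age mix but leave selection within each stratum.

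**Conclusion.** The mismatch stands on the text. SAP 2.1.1 names an effect for all treated participants, while each yearly AHV mean is conditional on still being in the study and can be shifted upward by who remains. Separately, the SAP omits the protocol's rule for leavers, so a child who leaves mid-year for slow growth has no AHV for that year.

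The size cannot be derived from the documents. The figures above rest on assumed means, correlations and exit rates, on full application of the slow-growth rule, and on carrying the first-year planning SD of 2.5 (or an assumed 1.5) into later years. They suggest a negligible shift in early years and a larger one only if mean growth nears 2 cm/year. Because the extension is descriptive, the risk is a misread trend, not a wrong test. The change is worth considering and is not essential.

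**What to change.** 1. **SAP 2.1.1:** describe the estimand as while in study, or conditional on remaining in study, unless heights after discontinuation are to be collected.
2. **SAP 3.1.1 and 5.3:** reconcile with Protocol 8.3 and 8.6.5, so that the exit-visit height gives the leaver an annualised height velocity in the exit year. State a minimum interval, because annualising magnifies measurement error: 0.2 cm, the repeat tolerance in Protocol Appendix C, becomes 0.2/0.25 = 0.8 cm/year over three months and 0.4 over six. List leavers with shorter intervals and their reasons.
3. **SAP 6.1.1:** add the within-child change in AHV from the previous year among children with both years. The same children then enter both sides of each comparison. AHV by baseline age stratum is an optional addition. Peak-GH tables are not needed, since no link between peak GH and leaving is shown.
4. **SAP 6.3:** reconcile its wording with the antibody sub-groups already planned in 6.1.1.

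The cost is SAP wording and a few descriptive tables from data already planned, with small cells in late years. The paired change still covers only children with both values, so item 1 is needed even if items 2 and 3 are adopted. No clinical withdrawal rule changes.
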